### 3.3. Special Patient Population

As required by MFDS guidelines, if any of the following special patient population is identified, sub-group analysis will be conducted for:

- Geriatric subjects (aged  $\geq$  65 years)
- Subjects with renal impairment
- Subjects with hepatic impairment

### 3.4. Long-Term Surveillance Case

Subjects who are treated with Xeljanz® for at least 52 weeks will be classified as long-term users.

#### 3.4.1. Long-Term Safety Analysis Set

Subjects belonging to the safety analysis set and who are treated with Xeljanz® for at least 52 weeks will be classified as long-term safety analysis set.

The cases below shall be excluded from the long-term safety analysis set in the following order:

- 1) Subjects who are excluded from the safety analysis set
- 2) Subjects who have been administrated Xeljanz® for less than 52 weeks (364 days)

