5. RATIONALE AND BACKGROUND

Xeljanz® (tofacitinib) is a potent, oral janus kinase inhibitor. Xeljanz was initially approved by the Ministry of Food and Drug Safety (MFDS) on 02 April 2014 for the treatment of adult patients with moderately to severely active rheumatoid arthritis (RA) who have had an inadequate response or intolerance to methotrexate. On 20 September 2019, new indications for the treatment of adult patients with moderately to severely active ulcerative colitis (UC) and psoriatic arthritis (PsA).

In clinical trials conducted on patients with moderately to severely active ulcerative colitis, the Xeljanz® (tofacitinib) demonstrated its efficacy and safety in adult patients who have had an inadequate response or intolerance to the basic treatments or biological agents. Ulcerative colitis has the chronic nature of relapse and improvement, most patients experience a number of acute deterioration throughout their life, and in the course of treatment with various drugs, they become resistant to or lose response to the treatment. Currently, there are very limited treatment options available to patients with moderately to severely active ulcerative colitis in terms of efficacy, safety, convenience of administration and quality of life (QoL). Therefore, for patients with limited options who do not respond to current available drugs, there are still many unmet needs for effective and rapid medications with new mechanisms of action.

CCI

Patients who are treated with Xeljanz for at least 52 weeks will be classified as long-term users. Out of all the enrolled patients, at least 18 cases (20%) of long-term users will be followed up to see the long term safety and effectiveness of Xeljanz. This non-interventional post-marketing surveillance (PMS) study is a commitment to MFDS.

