#### 3.4.2. Long-Term Efficacy Analysis Set

Subjects belonging to the long-term safety analysis set and whose efficacy data are available after 52 weeks ( $\pm 15$  days) of treatment will be classified as long-term efficacy analysis set.

The cases below shall be excluded from the long-term efficacy analysis set in the following order:

- 1) Subjects who are excluded from the long-term safety analysis set

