### 6.4. Long-Term Surveillance Case Analyses

The following analyses will be performed for long-term user who are treated with Xeljanz® for at least 52 weeks.

1) Safety analyses for long-term user

Safety analyses for long-term user will be performed based on data of long-term safety analysis set.

Repeated [6.2. Safety Analyses] - 1) ~ 4).

2) Efficacy analyses for long-term user

Efficacy analyses for long-term user will be performed based on data of long-term efficacy analysis set and analysis at week 52 ( $\pm 15$  days) will be added.

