## ***Statistical Analysis Plan for rPMS***

Repeated [6.3. Efficacy Analyses] - 1) ~ 7).

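### Long-term users must by definition have had 52 weeks on drug, so the planned account of 52-week non-completion among them is empty as written

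*SAP*

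**What the plan says.** **Who is a long-term user.** Protocol section 5: "Patients who are treated with Xeljanz for at least 52 weeks will be classified as long-term users". SAP 3.4 uses the same rule: subjects treated "for at least 52 weeks will be classified as long-term users". SAP 3.4.1 then excludes from the long-term safety set "Subjects who have been administrated Xeljanz® for less than 52 weeks (364 days", and SAP 3.4.2 nests the long-term efficacy set inside it: "Subjects belonging to the long-term safety analysis set and whose efficacy data are available after 52 weeks". The unredacted text gives no other definition, such as entry into extended follow-up.

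**What is planned for those who stop.** Protocol 7.7.2 calls for the cause of discontinuation in long-term users who fall short of 52 weeks. SAP 6.1.6 calls for counts and percentages of completion, at 24 weeks in general and at 52 weeks for long-term users, and for reasons in those who did not complete. The CRF item in protocol 7.2.5.1 is ticked yes on the same split; otherwise it is ticked no with one of three reasons (AE, lack of effectiveness, other). Protocol 7.2.5 and 7.3.3 and SAP 4.2 also foresee patients who do not reach 24 or 52 weeks, and use their last assessment.

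**What the long-term results cover.** SAP 6.4: "The following analyses will be performed for long-term user who are treated with Xeljanz® for at least 52 weeks". Safety is "Repeated [6.2. Safety Analyses] - 1) ~ 4" and efficacy is "Repeated [6.3. Efficacy Analyses] - 1) ~ 7". The protocol's stated purpose is that "at least 18 cases (20%) of long-term users will be followed up to see the long term safety and effectiveness of Xeljanz".

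**The concern.** The definition looks back from week 52, whereas the completion analysis needs a group identified before week 52, some of whom then stop. The plan never names that second group. Two things follow.

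- A programmer who applies the definition will produce a table showing full completion and no reasons. A reader could take it as a finding about persistence when it is only a consequence of the rule.
- Long-term status is not known until day 364, but the CRF completion item depends on it earlier. Sites therefore have no common rule for a patient who stops between weeks 24 and 52.

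At stake is the planned description of who came off drug in the second half of the year and for what reason. The SAP 6.4 results need to be read beside that description.

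**Working it through.** **1. The threshold.** 52 × 7 = 364 days, which reproduces the figure in SAP 3.4.1. Likewise 24 × 7 = 168 days. SAP 6.1.5 counts days on drug as end − start + 1, summed over treatment records.

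**2. The planned table.** Let T be days on drug.

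- Long-term users: T ≥ 364.
- Those who have not completed 52 weeks: T < 364.
- Subjects in both groups: 0, whatever the distribution of T.
- Completion among long-term users = n(T ≥ 364) / n(T ≥ 364) = 100%.

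The 24-week clause of SAP 6.1.6 is not affected.

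**3. One patient.** Take a hypothetical patient treated without interruption whose last dose is on day 250. Since 168 ≤ 250 < 364, this patient has completed 24 weeks and is not a long-term user.

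| Reading of the CRF item (protocol 7.2.5.1) | Completion tick | Reason recorded |
|---|---|---|
| Definition applied literally: the 24-week standard applies | yes | none |
| Site was following the patient towards 52 weeks and applies that standard | no | AE, lack of effectiveness or other |

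The second reading has support in protocol 7.2.5 and 7.3.3 and SAP 4.2, which provide for a patient who does not complete 52 weeks. Nothing in the text tells a site which reading to use.

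**4. Where that patient appears.**

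| Analysis | Day-250 patient |
|---|---|
| Main safety set (SAP 3.1, 6.2) | Eligible: early stopping is not an exclusion, and 6.2 takes all AEs recorded after administration during the study, including those that led to permanent discontinuation |
| Main efficacy set (SAP 3.2, 6.3) | Eligible: 250 days exceeds the 56-day minimum; contributes the investigator's final assessment and change to last value, subject to the other exclusions |
| Lack of efficacy on the CRF (protocol 9.1) | Recorded whether or not there is an associated AE |
| Long-term safety and efficacy sets (SAP 3.4.1, 3.4.2, 6.4) | Excluded on either reading |
| 52-week reasons table (SAP 6.1.6) | Absent on the literal reading; otherwise depends on the site's tick |

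Because SAP 6.4 repeats the action-taken table of SAP 6.2, the permanent-discontinuation row of its long-term version cannot contain anyone who stopped for good with under 364 days on drug. The main-set version can.

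**5. What cannot be computed.** The documents give no persistence or discontinuation rate between weeks 24 and 52. Neither the number of such patients nor any shift in the long-term results can be derived. The results in step 2 need no such rate.

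**The case against.** The strongest reply is that the restriction to patients with 52 weeks of exposure is declared openly, in SAP 3.4, 3.4.1 and 6.4. The study is descriptive and has no comparator, and protocol 7.8 says that its form is set by regulation. A 52-week exposure subset shown beside a full safety set is a legitimate display, and step 4 shows that early stoppers are not lost from the main analyses.

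That stands, and it limits the point. It does not remove the conflict, because openly declaring the subset does not supply subjects for the non-completion analysis that both documents promise.

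A second reply is that wording changes now cannot alter what was collected: SAP version 1.1 is dated 02 November 2022, after the planned end of data collection on 19 September 2022. That also stands. The remedy therefore has to work from recorded CRF fields, and some reasons will be missing.

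A third reply concerns remedies that go further, such as rebuilding the long-term analysis on everyone followed beyond week 24. Protocol 7.2.5 collects data to week 24 unless the patient is a long-term user. The week-24 window in SAP 6.3 is ±15 days and so runs to day 168 + 15 = 183, and SAP 5.2.2 sets the end date of an ongoing patient to the last follow-up. A routine 24-week patient seen on days 169 to 183 would enter such a cohort although no extended follow-up was intended, and an AE window to week 52 would cover time when no data were being collected. This objection is sound, and no such redesign is proposed.

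**Conclusion.** The conflict is real and explicit in the current text of both documents. Its certain size is 0 non-completers and 100% completion in the 52-week part of SAP 6.1.6 under the stated definition. If sites used the other reading, the content of the reasons table depends on site practice. The main loss is the tabulated account of stops between weeks 24 and 52. How many patients that concerns is unknown. The conclusion assumes that no redacted passage holds a second definition of long-term user.

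Two stronger inferences are not supported:

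- *That the safety or effectiveness data of early stoppers disappear from the study.* They remain eligible for the main sets. SAP 4.1 ties the 52-week AE window to long-term users, so how completely later events in an early stopper were collected is less clear, but no rule removes an event that was recorded.
- *That the long-term results conceal a selection of known size or direction.* The selection is stated, and the documents give nothing from which to estimate its effect. The results need a label so that they are not read as describing everyone who went on past week 24.

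How the 364-day rule fits with the ±15-day week-52 window is a separate question.

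**What to change.** 1. **Reconcile the definition.** Bring protocol section 5 and SAP 3.4 to 3.4.1 into line with protocol 7.7.2 and SAP 6.1.6, so that the group whose 52-week completion is reported can contain patients who stop.

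2. **Replace the 52-week part of SAP 6.1.6** with one table over the safety set. It takes patients who had not stopped by week 24 and classifies them by calendar time from first dose:
   - reached 52 weeks on drug;
   - final recorded stop date after week 24 and before week 52, with the recorded reason or *not recorded*;
   - no stop date and last follow-up before week 52, in a separate *ongoing / follow-up ended* row and not counted as non-completers.

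   Use the recorded stop date (protocol 7.2.5.3), not the end date imputed under SAP 5.2.2. Calendar time is needed because the SAP 6.1.5 duration sums treatment periods, so an interrupted patient who stopped after week 52 could have under 364 days on drug. Give 52-week completion only as reached / (reached + stopped), with the ongoing count beside it.

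3. **Keep the 364-day long-term sets**, and label their safety and effectiveness results as describing patients who stayed on drug for 52 weeks. Leave the AE window and the long-term analysis cohort as they are.

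The cost is some wording in both documents and one table from existing CRF fields. Some reasons will be unrecorded and cannot be recovered, and the 52-week completion figure may be less favourable than the automatic 100%.

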#### 3.4.2. Long-Term Efficacy Analysis Set

Subjects belonging to the long-term safety analysis set and whose efficacy data are available after 52 weeks ( $\pm 15$  days) of treatment will be classified as long-term efficacy analysis set.

The cases below shall be excluded from the long-term efficacy analysis set in the following order:

- 1) Subjects who are excluded from the long-term safety analysis set

## **Statistical Analysis Plan for rPMS**

- 2) Subjects without general efficacy assessment by the investigator
- 3) Subjects who are evaluated general efficacy assessment as 'Not assessable' by the investigator

### 3.5. Population Excluded from Safety Analysis

Population excluded from safety analysis will be reported separately with descriptive analysis only (number, percentage of subjects with adverse events and number of adverse events). However, subject who have not been administered for Xeljanz® will be excluded from this analysis set.

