## 3. Analysis Populations

### 3.1. Safety Analysis Set

Safety analysis set will be included all patients registered for this study who are prescribed at least 1 dose of Xeljanz® according to the local label and followed up for safety data.

The cases below shall be excluded from the safety analysis set in the following order:

- 1) Subjects who have been administered Xeljanz® prior to the contract date
- 2) Subjects who have not been administered Xeljanz®
- 3) Subjects who have not met the inclusion/exclusion criterion
- 4) Subjects who have not been evaluated for any safety-related endpoints

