## Statistical Analysis Plan for rPMS

- 5) Subjects who have any other significant protocol violation

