## **Statistical Analysis Plan for rPMS**

- 4) Analysis of factors that affect the safety
  - In the re-examination report, logistic regression of multivariate analysis will be performed and an odds ratio with 95% C.I and p-value will be presented to identify the factors that affect incidence of adverse events in demographic and other baseline characteristics.
- 5) Analysis for special patient populations [geriatric subjects (aged  $\geq$  65 years), subjects with renal impairment, subjects with hepatic impairment]
  - Adverse events and adverse drug reactions collected in each special patient population will be presented the number of subjects having adverse events, incidence of adverse events and the number of adverse events for each SOC and PT.
- 6) Analysis for population excluded from safety analysis
  - All adverse events investigated after administration of Xeljanz® for population excluded from safety analysis will be summarized with the number of subjects having adverse events, incidence of adverse events with 95% C.I and the number of adverse events by categorizing as follows.
    - Serious adverse events and serious adverse drug reactions (in the re-examination report only)
    - Unexpected serious adverse events and unexpected serious adverse drug reactions (in the re-examination report only)
    - Unexpected adverse events and unexpected adverse drug reactions (in the re-examination report only)
    - Adverse events and adverse drug reactions

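### AE incidence in patients excluded from the safety set is computed over a denominator that still holds treated patients with no safety evaluation, a group the main safety set removes

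*SAP*

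**What the plan says.** SAP 3.1 builds the safety analysis set by removing patients for five reasons, applied in order. Reason 1 is dosing that began before the contract date, reason 2 is never having been dosed, and reason 3 is failure to satisfy the eligibility criteria. Reason 4, the one at issue, reads "Subjects who have not been evaluated for any safety-related endpoints". Reason 5 covers any further major departure from the protocol.

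SAP 3.5 then gives the removed patients a table of their own, described as "descriptive analysis only (number, percentage of subjects with adverse events and number of adverse events"). It makes one carve-out: "However, subject who have not been administered for Xeljanz® will be excluded from this analysis set".

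SAP 6.2 item 6 carries this out: "All adverse events investigated after administration of Xeljanz® for population excluded from safety analysis will be summarized". The statistics listed there are the number of subjects with AEs, the incidence with a 95% CI, and the number of AEs. No further restriction on the population is given. SAP 5.2.1 allows no imputation apart from the date rules in 5.2.2, so a patient without safety data is not assigned an AE status. The protocol does not define an analysis of the excluded population.

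**The concern.** The carve-out in SAP 3.5 covers reason 2 and leaves reason 4 in. A patient with a recorded AE has been evaluated for safety, so a reason 4 patient can only add to the denominator. The SAP accepts this principle elsewhere: the main safety set requires safety follow-up and drops the unevaluated, and SAP 3.5 itself drops patients who could not have had an AE after dosing. The two AE incidences in the same report therefore follow different denominator rules, and a reader who sets them side by side is not comparing like with like.

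Reason 4 could well occur here. SAP 2.2 and Protocol 7.1 mandate no visits and describe AE assessment as running from the first dose to the next visit. A treated patient who does not return may have no safety evaluation at all.

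**Working it through.** The documents give no count or incidence for the excluded population, and SAP 2.4 says sample size calculations are not applicable. There is no plan figure to reproduce; the check is set logic followed by an illustration.

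**Who is in the SAP 3.5 set**

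| SAP 3.1 reason | In the 3.5 set? | Can contribute an AE? |
|---|---|---|
| 1 dosed before contract date | yes | yes, if evaluated |
| 2 never dosed | no | not applicable |
| 3 eligibility not met | yes | yes, if evaluated |
| 4 no safety endpoint evaluated | yes | no |
| 5 other significant violation | yes | yes |

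Because the reasons are applied in order, a patient coded 1 or 3 may also lack any safety evaluation. A patient coded 5 has already passed reason 4. The unevaluated group is therefore all of reason 4 plus an unknown part of reasons 1 and 3.

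**Formula.** Let N be the number of treated excluded patients, m the number of those with no safety evaluation, u = m/N, and x the number with an AE.

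- As written: x/N
- Among the evaluated: x/(N-m)
- Ratio: (N-m)/N = 1-u

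So u = 10%, 25%, 50% and 75% give ratios of 0.90, 0.75, 0.50 and 0.25, and u = 0 gives 1.

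**Illustration.** Assumptions, none of them from the documents: N = 40, and an AE incidence of about 40% among the evaluated (x rounded to a whole patient). Intervals are exact Clopper-Pearson 95% CIs; the SAP names no interval method.

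| u | m | x | As written, x/40 | Evaluated only, x/(40-m) |
|---|---|---|---|---|
| 10% | 4 | 14 | 35.0% (20.6 to 51.7) | 14/36 = 38.9% (23.1 to 56.5) |
| 25% | 10 | 12 | 30.0% (16.6 to 46.5) | 12/30 = 40.0% (22.7 to 59.4) |
| 50% | 20 | 8 | 20.0% (9.1 to 35.6) | 8/20 = 40.0% (19.1 to 63.9) |
| 75% | 30 | 4 | 10.0% (2.8 to 23.7) | 4/10 = 40.0% (12.2 to 73.8) |

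At u = 50% the interval as written is 35.6 - 9.1 = 26.5 points wide, against 63.9 - 19.1 = 44.8 points. It is lower, and it is also narrower because it counts 40 patients as observed when 20 were.

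**What the data cannot settle.** If every unevaluated patient had an unseen AE, the incidence among all treated excluded patients would be (x+m)/N. At u = 50% that is (8+20)/40 = 70%. The all-treated incidence could thus lie anywhere from 20% to 70%, and 40% is one value in that range.

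**The case against.** Several points on the other side stand.

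- The size is assumed. If no treated excluded patient lacks a safety evaluation, nothing changes.
- The table is secondary and descriptive. The number of subjects with AEs and the number of AEs are also reported, and neither depends on the denominator, so no AE is hidden.
- The evaluated-only incidence is not shown to be the true one. Recording an AE itself makes a patient evaluated, so restricting to the evaluated may push the figure up. The all-treated figure is a floor.
- SAP 8.1 refers to dummy tables that are not in the text supplied, and neither 3.5 nor 6.2 item 6 spells out a denominator. A footnote may exist there.

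A reader might infer that this table is the only check on whether the exclusions flatter the primary incidence, and that the dilution makes excluded patients look safer than they are. The documents do not support that. The SAP plans no comparison of this table with the safety set, and it pools unlike exclusion reasons.

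The objection that either denominator is a matter of taste does not stand. SAP 3.1 has already made the choice for the main set by removing the unevaluated, and SAP 3.5 departs from it without giving a reason. Nor can a reader be sure of recovering the evaluated figure. Protocol 7.7 promises numbers enrolled, retrieved and analysed, but not counts by exclusion reason. Even such counts would miss unevaluated patients coded under reasons 1 and 3.

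**Conclusion.** The concern holds as an inconsistency between SAP 3.1 and SAP 3.5 that carries into 6.2 item 6. As the sets are defined, the excluded-population AE incidence is (1-u) times the incidence among evaluated excluded patients, and its 95% CI treats unobserved patients as observed and free of AEs. Relative to the evaluated incidence the shift can only be downward. Its size is unknown: 0.90 to 0.25 of the evaluated incidence for an assumed u of 10% to 75%, and none if u is zero.

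This rests on two readings: that the percentage is taken over the set as SAP 3.5 defines it, and that a recorded AE counts as a safety evaluation. It does not reach the primary safety-set incidence, because SAP 3.1 removes unevaluated patients there. The evaluated-only value should not be presented as the correct incidence. The case for it is that it follows the rule already used in the main set.

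**What to change.** In SAP 3.5, and to match in 6.2 item 6, define the denominator as treated, excluded patients with at least one safety evaluation, whatever their coded exclusion reason. Removing only those coded reason 4 would leave unevaluated patients under reasons 1 and 3 in place.

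Report the number of treated, unevaluated patients separately, so that the all-treated percentage can also be derived, and show the counts by exclusion reason. The same edit can reconcile SAP 3.5, which lists only numbers and percentages, with 6.2 item 6, which adds a 95% CI.

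The cost is about one sentence in the SAP, a changed denominator and a footnote, with no new data. The downside is that reading the evaluated-only incidence as that of all treated excluded patients assumes the unevaluated resemble the evaluated. The separate count makes visible how many patients that assumption covers.
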